3.4.4.2 Partner Self-Testing

Index clients will provide their partners with the following instructions verbally. The following instructions will also be provided on the referral form in picture form and in the local language:

1. Complete HIV self-test
2. If the self-test is positive, bring the self-test kit and referral card to the clinic for confirmatory testing and linkage to care.
3. If the self-test is positive and the client does not wish to present for further care, the self-test kit should be disposed of in the lockbox at the HSA house.
4. If the test is negative, the client will be instructed to dispose the self-test kit in a lockbox at the HSA house in the local community or may bring the kit to the lockbox at OPD/STI.

Any individual who has difficulty with the self-test kit or needs help with interpretation can come to the facility with the kit and the referral card and be seen by an HDA for assistance and/or standard of care HIV testing.

3.4.4.3 Follow-up of Partner Self-Testing

The number of index partners tested will be determined based on the number of self-test kits returned to village and health facility lockboxes and triangulated with self-reports from a follow-up survey with the index client. Additionally, partners with a positive self-test kit who present to the facility for confirmatory testing and linkage to care, and/or partners who did not use the self-test kit but present to the facility for HIV testing will be accounted for through the returned referral cards. Like self-test kits, referral cards will be identified with a unique code, allowing the partner to be linked to the index client.

For those who are HIV-positive and present to the clinic for care, the ART register will be reviewed four weeks later to determine if the patient starts ART and presents for their four-week follow-up visit. All data from registers will be anonymized for use by the study team. In addition, index clients will provide self-reports about partner linkage to ART during a follow-up survey.

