3.3.1. Description of Randomization and Study Arms

Randomization from Aim 1 will be accomplished such that facilities randomized to the self-test intervention in Aim 1 will be self-test intervention sites for Aim 2 and sites randomized to standard of care and optimized standard of care for Aim 1 will continue as standard of care and optimized standard of care sites for Aim 2.

Description of Study Arms

1. **Standard of care arm:** Facilities randomized to the standard of care arm will use MOH approved referral mechanisms, without any intervention from the study team. Standard of care quality will vary by facility and may include some level of partner referral services for index partners such as referral slips. Referral slips may be given at HIV testing or ART clinics. Sites will be asked to counsel clients to have their partners bring referral slips back to the clinic to document the number of partners presenting for HIV testing. A random subset of HIV-positive clients in the standard of care arm will complete an anonymous survey to answer questions about whether they used referral slips and whether they know if partners came to a health facility for testing.

2. **Optimized standard of care arm:** Facilities randomized to optimized standard of care will be supported by the study team to systematically perform referral services following Ministry of Health Guidelines. Providers will receive an initial refresher training on partner testing followed by regular mentoring visits. Job aids will also be used to remind providers about the importance of partner testing. Standard of care procedures involve counseling HIV-positive individuals about the importance of partner testing and providing ‘referral slips’ to the index client to distribute to every sexual partner within the prior 12 months. Referral slips will be used to encourage partners to come to the facility for HIV testing. Sites will be asked to counsel clients to have their partners bring referral slips back to the clinic to document the number of partners presenting for HIV testing. A random subset of participants in the optimized standard of care arm will complete an anonymous survey to answer questions about whether they used referral slips and whether they know if partners came to a health facility for testing.

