4.2. Optimized Standard of Care Arm

4.2.1. Partner Notification and Referral

The study team will provide trainings, job aids, and regular mentorship to promote optimized standard of care in regards to partner notification and referral strategies for HIV-positive clients with partners who have an unknown HIV status. Under optimized standard of care, providers will ask clients at every ART visit whether they have current or recent (within 12 months) sex partners with unknown HIV status or tested negative for HIV more than 6 months ago. Clients will be counseled on the importance of partner notification and testing and given a partner notification slip to assist in partner notification and testing referral. Individuals will be counseled to ask their partners to return the referral slips when they come for testing. Partners who present at the facility for HIV testing will be tested in private rooms by trained HDAs following Ministry of Health guidelines. HDAs will ask all clients presenting for testing whether they were referred by a partner and this will be indicated in a column in the HIV testing register. Serial HIV testing will be performed with Determine and Uni-Gold as per standard of care. Those that test positive will be counseled and referred to ART services. ART initiation will follow standard clinic protocols under the universal treatment (Test and Treat policy).

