3.4.2.2 Baseline Visit for Index Client

A random sample of individuals will be screened and consented as they exit their ART visit. This will include ART clients who report having a sexual partner with an unknown HIV status. After written informed consent has been obtained, study staff will collect basic socio-demographics (including age, gender, marital status, and number of partners), HIV characteristics (date of HIV diagnosis, whether on ART and date started), and the number of eligible sexual partners who qualify for index testing referral slips. Individuals who consent will also be asked whether they were offered a referral slip on the day of the survey.

Follow-up Visit of Index Clients

All index clients will be seen by study staff when they come for their next ART follow-up visit. A brief survey will be performed to collect information about whether the client disclosed their HIV status to their sex partner(s), whether they gave referral slips to their partner(s), and knowledge about whether partners completed a test, knowledge of their partner's test result, and knowledge about their partner's linkage to care. We will also survey the index client to determine whether any gender-based violence or fear of gender-based violence resulted from use of the self-tests. Index clients who do not return for their ART follow-up visit (more than two weeks late) will be traced through standard site protocols and surveyed either in the community or at the facility, if they return to care.

HIV testing registers will also be reviewed to measure the number of individuals tested through partner referrals and the proportion of partner referral tests who were identified as HIV-positive. All registry data will be anonymized. Records from partner notification clients aged 15 years and older will be included in the study. For those who are HIV-positive, the ART register will be reviewed to determine if the patient started ART and presented for their four-week follow-up visit.

At the time of follow-up, a random sample of 40 index clients (20 men and 20 women) will be selected and asked to participate in semi-structured, in-depth interviews to explore the feasibility and acceptability of providing referral slips to partners, including challenges with disclosure and questions around harm or perceived risk of harm due to distributing the referral slip.

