5. STATISTICAL METHODS

5.1. Outcome Measures

3.5.1.1 Sample Size and Statistical Analysis for Primary Outcome Measures

We will have 15 clusters (facilities) available for randomization, and therefore, estimated our sample size assuming a fixed number of clusters (k) and an equal number of clusters per arm. We also assumed an equal number of participants per cluster. The below calculations were determined using a minimum sample size. Assuming a type I error of 0.05, an intracluster correlation of 0.004 and sample sizes of 600 HIV-positive patients per arm, we have 89% power to detect a difference in testing coverage of 20% in study arm 2 (optimized standard of care) and 40% in study arm 3 (self-testing). Because we are uncertain about the proportion of partners who will test under each arm, we have considered a range of possibilities, with the majority of scenarios providing at least 87% power to detect a difference between the two arms of interest (optimized standard of care and self-testing) (Figure 4).

We will calculate descriptive statistics, including mean/median, variation (standard deviation, kurtosis), range, and frequency distributions for the demographic and clinical characteristics, overall and by study arm. The outcomes of interest include the proportion of partners tested and HIV-positivity of partners. Differences in the prevalence of each of the outcomes of interest will be examined by study arm as well as by other factors of interest including demographic characteristics (e.g., age, gender), clinical characteristics (e.g., reason for clinic visit), and structural factors (e.g., geographic location). The differences will be evaluated using t-tests, Mann-Whitney U test (or other non-parametric tests), chi-square methods, and Fisher's exact test as appropriate. In order to assess factors associated with partner's HIV testing/positivity, we will use hierarchical linear models in order to account for clustering of effects within each clinic. Separate models will be developed for each outcome of interest and covariates of interest include patient characteristics (e.g., age, gender) and other structural and contextual factors.

Qualitative Analysis for Secondary Outcome Measures

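### Aim 2: partners tested are counted from different sources in the self-testing and optimized standard of care arms, and no rule makes the primary comparison like for like

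*Combined protocol and SAP*

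**What the plan says.** The primary objective in section 3.1.1 sets kits for partners against optimized standard of care with referral slips. Section 3.5.1.1 states: "The outcomes of interest include the proportion of partners tested and HIV-positivity of partners". It names no data source, denominator or rule for conflicting sources.

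**Self-testing arm.** Section 3.4.4.3 gives a counting rule: "The number of index partners tested will be determined based on the number of self-test kits returned to village and health facility lockboxes", with the count "triangulated with self-reports from a follow-up survey with the index client". Partners who come to a facility are counted through cards: "referral cards will be identified with a unique code, allowing the partner to be linked to the index client". Capture is helped by a phone line for collecting kits in the community (section 3.3.1) and by staff visits to nearby testing sites to look for returned cards (section 3.4.4.1).

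**Optimized standard of care arm.** No equivalent rule is given. Three sources are described:
- Clients are counselled to "have their partners bring referral slips back to the clinic to document the number of partners presenting for HIV testing" (section 3.3.1). The slips are not said to be coded.
- "HDAs will ask all clients presenting for testing whether they were referred by a partner and this will be indicated in a column" of the testing register (section 4.2.1). Under the follow-up visit in section 4.2, "HIV testing registers will also be reviewed to measure the number of individuals tested through partner referrals" and "Records from partner notification clients aged 15 years and older will be included in the study". These data are anonymized, and no link to the surveyed index clients is described.
- Index clients are asked at their next ART visit whether they know that partners tested.

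**Common to all arms.** The index follow-up survey is planned in each arm (sections 4.1, 4.2 and 3.4.4.4), with tracing of clients who are late. At baseline every arm records the number of partners. The further item on eligible partners differs: under optimized care it counts those who qualify for slips, and under self-testing it counts those to whom the client intends to give kits.

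**The concern.** A superiority comparison needs the same endpoint in both arms. The only counting rule in the plan starts from an object, the returned kit, that exists in one arm. An analyst who follows it would count kits and coded cards in self-testing, and would have to choose among survey, slips and registers in the optimized arm. These sources can miss or add tests for different reasons:

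- A kit that is used but never returned lowers the self-testing count.
- A slip that is not brought back, or a test at another facility, lowers the optimized count.
- Register entries for partners of clients outside the surveyed sample raise the optimized count and do not match a survey-based denominator.
- A denominator of partners to whom the client intends to give kits leaves out eligible partners the client will not approach, which raises self-testing coverage.

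The primary contrast is at stake. So are the average cost per partner tested and the incremental ratio in the Aim 2 cost-effectiveness sections (6 and 6.2), which use the same count.

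**Working it through.** **Side by side, primary contrast only**

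| | Optimized standard of care | Self-testing |
|---|---|---|
| Stated counting rule | none | returned kits, checked against index report, plus cards |
| Physical record | slips, not stated to be coded | kits and cards with IDs tied to the index client |
| Register | anonymized referral counts, no described link to the sample | ART register used for linkage to care |
| Search outside the facility | none stated | community kit collection; visits to nearby sites |
| Index follow-up survey | yes | yes |
| Eligible-partner item at baseline | qualify for slips | client intends to give kits |
| Source that prevails | not stated | not stated when sources disagree |

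**Inputs.** Section 3.5.1.1 gives 600 per arm, ICC 0.004, type I error 0.05, and 20% versus 40%. Fifteen clusters over three arms give k = 5 per arm and m = 600/5 = 120 per cluster. My assumptions are a two-sided test (sidedness is not stated), one eligible partner per client, equal clusters, and every capture share below.

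**Formulas.** Design effect = 1 + (m − 1) × ICC = 1 + 119 × 0.004 = 1.476. SE = √{[p₀(1 − p₀) + p₁(1 − p₁)] / 600 × 1.476}. Measured coverage = true coverage × capture share. Each result is given for noncentral t with 8 df (critical value 2.306) and for the normal (1.960).

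**The plan's own figure.** For 20% versus 40%, SE = √[(0.16 + 0.24)/600 × 1.476] = 0.0314 and 0.20/0.0314 = 6.38, so power exceeds 99%. The stated 89% is not reproduced at ICC 0.004. That is a separate matter, and this point does not depend on it.

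**Illustrations at ICC 0.004**

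| True coverage (optimized vs self-testing) | Assumed capture | Measured | SE | Difference/SE | Chance of significance (t / normal) |
|---|---|---|---|---|---|
| 20% vs 20% | 90% in one arm | 18% vs 20% | 0.0275 | 0.73 | 10% / 11% |
| 20% vs 20% | 80% in one arm | 16% vs 20% | 0.0269 | 1.49 | 26% / 32% |
| 20% vs 40% | 90% in self-testing | 20% vs 36% | 0.0310 | 5.16 | 99% / >99% |
| 20% vs 40% | 80% in self-testing | 20% vs 32% | 0.0305 | 3.94 | 93% / 98% |
| 20% vs 40% | 70% in self-testing | 20% vs 28% | 0.0298 | 2.68 | 65% / 76% |

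In the first two rows the false result favours whichever arm is better captured.

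**Sensitivity to the ICC.** A larger ICC leaves the shift in measured coverage unchanged but makes the test less sensitive. At 0.04, a value I assume and the documents do not give, the design effect is 1 + 119 × 0.04 = 5.76. The first, second and last rows become 6–7%, 10–12% and 22–27%.

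**The case against.** The sources overlap. Every arm plans an index follow-up survey with tracing, and section 3.4.4.3 checks kit returns against it. A reader might infer that the plan has no comparable measure of partner testing; the documents do not support that. What stands is that the survey is the cross-check in the only stated rule, and that the statistical section does not make it primary. The Aim 1 statement that all arms use the same data collection (section 2.4) does not extend to Aim 2.

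A reader might also infer that the counting favours self-testing. That is not shown. Community collection and visits to nearby sites recover tests that took place, so they move that count toward the truth. They distort the contrast only if comparator capture is lower, and no figure in the documents says so. Unreturned kits work the other way.

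Index clients may receive kits for themselves, and the kit IDs link to the index client, so an own kit could be taken for a partner test. A large inflation from this is not supported. Own kits are meant for couples testing, staff record the numbers of partners and kits, and the survey gives a check.

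If the planned effect is real and the stated ICC is right, modest under-capture does little harm: at 80% capture in self-testing, power is still 93–98%. The illustrations rest on assumed shares. Both points stand. They limit the size of the problem but do not supply the missing rule.

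**Conclusion.** The concern holds in this form. For self-testing versus optimized standard of care, the plan states a counting rule that only one arm can use, names no lead source for the other arm, gives no rule for disagreement, and words the item on eligible partners differently. Measured coverage can therefore differ by arm for reasons other than partner testing, in a direction that cannot be known beforehand.

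Under the assumed shares, the size runs from slight (10–11% false significance at 90% capture in one arm) to material (26–32% at 80%, or power of 65–76% at 70% capture in self-testing). These figures assume ICC 0.004, one partner per client and a two-sided test. They show what is possible and do not estimate what will happen.

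Differences in how the standard of care arm records partners do not affect the primary contrast. This should be fixed before analysis. It does not show that the result will be wrong.

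**What to change.** 1. Define the primary outcome identically in all arms and name the source that prevails. The simplest choice is each eligible partner listed at baseline who is reported tested at the index follow-up survey, counted once, with a stated rule for clients who are not followed up. Use kits, cards, slips and registers for validation or prespecified sensitivity analyses.
2. Ask the same baseline question on eligible partners in every arm, using the definition in section 3.2.1, and make that list the denominator.
3. As a minor safeguard, log each kit ID by intended user so that index clients' own kits are left out of partner counts.

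The cost is low: protocol and survey wording plus a kit log. The survey is already planned in every arm.

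The downside is that index report is unblinded and its accuracy may differ by arm. Consent withholds outcome detail in the two comparator arms (Informed Consent, under section 3.3.2), and compensation for Aim 2 participation is stated only for the self-testing arm (section 7.4). The sensitivity analyses would examine this. Another single source would also serve if it is available and linked in every arm.

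Separately, the comparator survey is called anonymous in sections 3.3.1 and 3.3.2, with oral consent in 3.3.2. Sections 4.1 and 4.2 require written consent, follow-up and tracing. These passages should be reconciled so that baseline and follow-up responses can be linked.

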3. **Partner self-testing arm:** Facilities randomized to partner self-testing will have study staff give self-test kits to index clients to distribute to every sexual partner with unknown status who lives in the facility catchment area within the prior 12 months (up to three sexual partners). They will also be given self-test kits for themselves so they can participate in couples testing if they choose. All index clients will be counseled on the importance of partner notification and testing and receive a demonstration on how to perform the self-test, so they can show partners. Self-test kits will contain information on how to use the test and a referral card. The referral card will contain information on where to present for confirmatory testing and where partners can receive ART, including a map to the facility. Index clients will be counseled to tell their partner to drop the completed test in a lockbox at the local health facility. A study phone number will also be provided in order to facilitate community-based collection of kits if participants are unwilling or unable to attend the facility. Written instructions, picture instructions, and maps will also be provided to the index client to give to the index partner. Index clients will also be counseled to encourage partners to present to the facility for routine HDA testing if they are unable or uncomfortable completing the self-test.

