4.3. Partner Self-Testing Arm

3.4.4.1 Baseline Visit for Index Client

A random sample of individuals will be screened and consented as they exit their ART visit. This will include ART clients who report having a sexual partner with an unknown HIV status. After written informed consent has been obtained, study staff will collect basic socio-demographics (including age, gender, marital status, and number of partners), HIV characteristics (date of HIV diagnosis, whether on ART and date started), and the number of eligible sexual partners they plan to give self-test kits.

The study staff will counsel the index client on how to administer an HIV self-test and will provide one self-test kit for each sexual partner within the last 12 months with unknown status (or HIV-negative more than 6 months ago) who lives within the catchment area of the facility and for whom the index client is willing to provide the test kit (up to three sexual partners). Index clients will also be given self-test kits for themselves if they wish to use them to complete couples counseling. All HIV self-test kits will be labeled with a unique ID linked to the index client participant. The ID will also be used to link index client survey responses with returned self-test kits.

The number of partners and the number of kits provided will be documented by study staff. Each self-test kit will be in a package that also contains a referral card. The referral card can be used for (1) those who test HIV-positive and need to present for confirmatory testing and link to care, (2) those who do not want to use the self-test kit and would rather test with an HDA, or (3) clients who experience difficulty or discomfort with the self-test kit and choose to test at a facility. The referral card will include information about the fa-

cility, including a map. The card will also contain a notation that if it is returned to another facility, the facility should contact the study team so that the card can be collected and recorded as “returned”. Study staff will periodically visit nearby testing sites to determine if any referral cards have been returned to those sites.

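### In Aim 2's self-testing arm, the returned-kit count can credit some index clients' own-use kits as partner tests, because no rule separates the two

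*Combined protocol and SAP*

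**What the plan says.** **How partner tests are counted.** Section 3.4.4.3 sets this rule: "number of index partners tested will be determined based on the number of self-test kits returned to village and health facility lockboxes and triangulated" against what index clients report at follow-up. Partners who come to a facility are picked up through the cards they hand in: "Like self-test kits, referral cards will be identified with a unique code, allowing the partner to be linked to the index client".

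**Kits for the index client.** Section 3.3.1 says of index clients: "They will also be given self-test kits for themselves so they can participate in couples testing if they choose". Section 3.4.4.1 repeats this: "Index clients will also be given self-test kits for themselves if they wish to use them to complete couples counseling".

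**What is recorded.** Section 3.4.4.1 gives one kit per eligible partner whom the client is willing to approach, up to three. It also records how many partners the client plans to give kits. On labelling, it says: "All HIV self-test kits will be labeled with a unique ID linked to the index client participant". On what that label is for, it adds: "The ID will also be used to link index client survey responses with returned self-test kits". On dispensing records, it says: "The number of partners and the number of kits provided will be documented by study staff". The follow-up survey in section 3.4.4.4 asks whether partners were given kits and completed the test. No listed item concerns the client's own kit.

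**The comparator.** The optimized standard of care arm has no kits. Under section 4.2.1, testing staff ask whether a person was referred by a partner, and "this will be indicated in a column in the HIV testing register". Its index clients get the same kind of follow-up survey.

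**The outcome.** Section 3.5.1.1 names the proportion of partners tested as an outcome of interest, and section 6.2 calls it the primary study outcome and uses it as an effectiveness measure. Neither section gives a counting rule, an exclusion for own-use kits, or an order of precedence among sources.

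**The concern.** The numerator in the self-testing arm starts from a count of returned kits, and the kits in circulation include some that were never meant for a partner. An own-use kit dropped in a lockbox carries an ID pointing to the same index client as the partner kits. Nothing in the text tells the person emptying the box to leave it out.

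Only one arm has kits, so this particular error can only raise the measured coverage of the self-testing arm. Partner testing is the Aim 2 primary outcome and feeds the cost-effectiveness ratio, so both would inherit it. The trial is also unblinded (Schema). A conflict between kit count and client report would be settled by a choice made after the arm is known, unless the rule is written first.

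**Working it through.** The plan gives no figure for own-kit returns, so there is none to reproduce. The planned comparison in section 3.5.1.1 (20% versus 40% coverage, 600 clients per arm) serves only as a yardstick. The stated power does not enter.

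**Step 1. What the existing records can and cannot do.**

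- Kits provided minus planned partner recipients gives the number of own-use kits each client took. Clients with no surplus kit carry no risk of this error.
- For a one-partner client, two returned kits exceed the recorded number of partners and stand out.
- An own kit returned when the client reports no partner test shows up through the ID-linked survey.
- For a client with three partners, an own kit plus one partner kit makes two returns, which is within the recorded number. The survey may show one reported partner test against two kits. That could be an own-use kit, or a second partner who tested without telling the client. The records do not say which, and no rule decides.

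**Step 2. Illustrative size.** Assumptions, none given by the documents:

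- u = share of clients whose own kit is returned, at most one each: 10%, then 5%.
- k = eligible partners per client, each given one kit: 1 or 3. Three is the maximum in section 3.3.1, not a stated average.
- p = share of partner kits returned: 20% or 40%, borrowed from the planned coverage figures.
- Credited tests are capped at k per client. The plan states no cap, but an outcome that is a proportion of partners implies one.
- Self-report corrects nothing.

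If own-kit and partner-kit returns are independent, an own kit adds a false credit unless all k partner kits also came back:

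added coverage = u(1 − p^k)/k

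If the own kit comes back only when at least one partner kit does:

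added coverage = (u/k) × [1 − p^k / (1 − (1 − p)^k)]

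With u = 10%, that is 60 own kits among 600 clients:

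| Partners per client | Return pattern | p = 20% | p = 40% |
|---|---|---|---|
| 1 (600 partners) | independent | 60 × 0.8 / 600 = 8.0 points | 60 × 0.6 / 600 = 6.0 points |
| 1 (600 partners) | together | 0 | 0 |
| 3 (1,800 partners) | independent | 60 × (1 − 0.008) / 1,800 = 3.3 points | 60 × (1 − 0.064) / 1,800 = 3.1 points |
| 3 (1,800 partners) | together | 3.33 × (1 − 0.008/0.488) = 3.3 points | 3.33 × (1 − 0.064/0.784) = 3.1 points |

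A simulation of the independent case with 1,000,000 clients gave the same 8.0, 6.0, 3.3 and 3.1.

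Every formula is proportional to u, so all values halve at 5%: at most 4.0 points with one partner, and about 1.6 to 1.7 with three. If self-report corrected half of the false credits, they would halve again.

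**Step 3. Direction.** Own-use miscounting pushes the self-testing arm up. Used partner kits that are never returned lower the kit count in the same arm. The documents give no rate for either, so the sign of the net error in the arm contrast cannot be derived.

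**The case against.** The best defence is that the plan already holds most of what is needed. The subtraction in Step 1 finds every client who took a surplus kit, so those clients can be bounded or set aside in a sensitivity analysis. Own kits are meant for testing with a partner, and a client who tests alongside a partner is well placed to say whether that partner tested. That is the situation in which the survey is most reliable and, with one partner and a cap, the error is about zero. Own kits are optional, index clients already know they are HIV-positive, and the return instructions in sections 3.3.1 and 3.4.4.2 are addressed to partners. Few own kits may therefore reach a lockbox. A recipient log could also sit in the site procedures that section 8.2 foresees.

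Most of this stands, and it rules out three stronger readings that a reader might infer:

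- *The count could not be repaired afterwards.* The documents do not support this. Planned recipients and kits provided are both recorded, so the affected clients can be identified and the error bounded.
- *Coverage could rise by 10 points at 10% own-kit return.* With one partner per client and no cap, 60/600 does give 10. That credits one partner with two tests, which does not fit an outcome defined as a proportion of partners.
- *The comparison is biased in favour of self-testing.* Only this one component has a known direction; unreturned partner kits work against it.

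What the defence does not supply is a way to tell which returned kit was the client's own, or a rule for settling a conflict between sources. Site procedures might add a log, but the protocol does not require one.

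**Conclusion.** The point holds in a limited form. The counting rule as written can credit some own-use returns as partner tests, and only in the self-testing arm. Existing records confine the error to clients with a surplus kit and would expose many cases, but they neither identify the own-use kit nor say how a conflict is resolved.

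The size is unknown and probably small: under the Step 2 assumptions at 10% own-kit return, about 0 to 8 points with one partner per client and about 3 with three. That would not by itself produce the planned 20-point difference, but it could shift the estimate and the cost-effectiveness ratio. No net direction for the contrast is claimed. This should be fixed, ideally before kits are handed out; it is not a fatal flaw.

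**What to change.** At hand-out:

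- Give own-use kits a distinct ID suffix.
- Log the intended recipient against each kit ID.

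In the outcome definition in section 3.5.1.1:

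- Exclude own-use IDs from the partner count.
- Count at most one test per eligible partner.
- State which source prevails when returned kits, referral cards and the index client's report disagree.

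In the analysis, add a sensitivity analysis that uses index-client report alone in both the optimized standard of care and self-testing arms. The follow-up surveys already planned in both arms collect this.

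The cost is a label suffix, one log column, a short definition and a little extra analysis. No participants, visits or survey items are added. The report-only analysis is limited by what index clients know about their partners' testing, so it serves as a check and does not replace the main count.
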